## **Statistical analysis**

The information is recorded in a database created with the Excel computer program. Statistical analysis is performed with Epi Info™ 7.2 software and R Studio version 1.3.1093.

For the descriptive analysis of the variables, the mean, standard deviation, minimum, and maximum values are calculated for the quantitative variables, and the relative frequencies and percentages are calculated for the qualitative variables.

For the study of the association between categorical variables, the chi-square statistic or Fisher's exact test is used when the data are independent, while for the related data the McNemar test is used for two groups, transforming the variables into dichotomous ones for its analysis. Stratified analysis is performed using the Mantel-Haenzsel test.

For the multivariate analysis, the logistic regression model is used, including the variables included in the analysis. The stepAIC function from the R MASS package is used.

To validate the results, in terms of significance, a confidence level of 95% is used and any value of  $p < 0.05$  is considered significant.

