### **Sample**

The estimated sample size for a difference between two proportions, with a statistical power of 80% for an alpha significance level of 0.05 with a prevalence of postoperative delirium of 30% and a rate of loss to follow-up of 10%, is 52 patients per group.

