### **Variables**

These consisted of sociodemographic variables such as age and gender, anthropometric weight, height, BMI. Social variables consisted of whether the patient lived alone or accompanied etc., as well as surgical, anesthetic and postoperative care characteristics such as the type of intervention, use of drugs, time mechanical ventilation or extracorporeal circulation, etc.

Variables related to postoperative delirium are also collected, such as the positive or negative result of the CAM-ICU scale, as well as those related to the projection of visual material, pharmacological measures or mechanical restraints used.

Finally, the objective score obtained in the Mini-mental State Examination (MMSE) is recorded in order to assess the patient's prior cognitive status.

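### Age and MMSE are collected on every patient, but the SAP fixes neither in the between-arm analysis and leaves adjustment to unnamed strata and an automatic search

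*SAP*

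**What the plan says.** The Variables section lists the baseline data: "These consisted of sociodemographic variables such as age and gender, anthropometric weight, height, BMI". It also gives the purpose of the cognitive test: "the objective score obtained in the Mini-mental State Examination (MMSE) is recorded in order to assess the patient's prior cognitive status". Development of the intervention confirms that every patient has the MMSE at the outset, whatever the group. It describes randomisation before it describes the MMSE.

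The Statistical analysis section offers four inferential tools:

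- A test for independent categorical data: "For the study of the association between categorical variables, the chi-square statistic or Fisher's exact test is used when the data are independent".
- McNemar's test for related data. The conversion of variables to two categories is mentioned in this clause only.
- A Mantel-Haenszel stratified analysis, with no strata named.
- A logistic regression on the variables in the analysis, which are not listed, using the stepAIC function.

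None of these is labelled as the main comparison of CAM-ICU between arms. Age and MMSE are not named in any of them.

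The Sample section sizes the trial for a difference between two proportions, "with a statistical power of 80% for an alpha significance level of 0.05", with delirium at 30% and 10% loss to follow-up. The result is 52 per group.

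**The concern.** Prior cognition and age are plausible predictors of postoperative delirium, and the SAP collects MMSE precisely to describe the former. A predictor of outcome that is measured on everyone can sharpen the arm comparison and protect it against chance imbalance, but only if its use is fixed beforehand.

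As written, whether age and MMSE are used, and in what form, would be settled after the data are seen. Mantel-Haenszel needs categories, and no cut-points are given. A stepwise search may drop either covariate or the arm term. It may also bring in postoperative variables such as drug use or ventilation time, which the Variables section lists too. At stake are a few points of power in a small trial, and a result that could lean on which arm happened to receive the older or cognitively weaker patients.

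**Working it through.** **Inputs.** From the SAP: alpha 0.05, power 80%, delirium 30%, loss 10%, 52 per group. Assumed: 30% is the control rate; the test is two-sided; and the prognostic strength of age and MMSE combined is an odds ratio (OR) of 1.0 to about 3.3 per SD of a standardised baseline index.

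**The SAP's own figure.** The second proportion is not stated, so 52 cannot be derived outright. One can solve for the rate that yields it.

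- Unpooled: n = (1.960 + 0.842)² × [p1(1−p1) + p2(1−p2)] / (p1−p2)². With 0.30 and 0.08: 7.849 × (0.2100 + 0.0736) / 0.0484 = 46.0, so 46. Then 46/0.9 = 51.1, so 52.
- Pooled, no continuity correction, 0.30 and 0.075: n = 47. Then 47/0.9 gives 53, and 47 × 1.1 gives 52.
- Other variants (continuity-corrected, one-sided) reach 52 or 53 with a second rate between 6% and 10%.

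The size therefore roughly implies 30% versus 8%. Evaluable patients: 52 × 0.9 = 46.8, about 47 per arm. Expected events: 47 × 0.30 + 47 × 0.08 = 14.1 + 3.8 = 17.9, about 18.

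**Power at 30% versus 8%** (simulated, 47 per arm, 4000 trials per row, likelihood-ratio test of the arm term, Monte Carlo SE about 0.6 point):

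| OR per SD of baseline index | Unadjusted | Adjusted | Gain (points) |
|---|---|---|---|
| 1.0 | 81.5% | 81.5% | 0 |
| 1.5 | 81.2% | 81.6% | 0.4 |
| 2.0 | 81.8% | 83.7% | about 2 |
| 3.0 | 82.4% | 87.5% | about 5 |

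**Power at 30% versus 12%** (3000 trials per row, two equally prognostic continuous covariates, crude chi-square against the adjusted model):

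| Log-OR per SD (OR) | Unadjusted | Adjusted | Gain (points) |
|---|---|---|---|
| 0.8 (2.2) | 58.2% | 62.8% | 4.6 |
| 1.2 (3.3) | 58.4% | 66.8% | 8.4 |

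Both rows assume fairly strong prognosis; weaker values would give less.

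**False positives with no arm effect.** Across these runs, chi-square rejected in 4.3 to 5.9% and the adjusted likelihood-ratio test in 4.7 to 5.9%. Both are near nominal, the adjusted test at most slightly liberal.

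**Chance imbalance.** The SD of a standardised baseline difference is √(2/47) = 0.206. The chance that it exceeds 0.25 SD in either direction is 2 × [1 − Φ(0.25/0.206)] = 23%. A difference above 0.3 SD arose in about 15% of simulated trials. Within those, at log-ORs of 0.8 and 1.2:

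- With no effect, false positives were about 7 to 13% unadjusted and 4 to 6% adjusted.
- At 30% versus 12%, unadjusted power was about 29 to 36% when the intervention arm was at higher risk and 78 to 84% when it was at lower risk. Adjusted power stayed at about 60 to 68% either way.

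**stepAIC.** One term stays in the model if its likelihood-ratio chi-square on 1 df exceeds 2. A term with no effect is therefore kept with probability P(χ²₁ > 2) = 15.7% and dropped otherwise. Nothing in the SAP exempts arm, age or MMSE from this rule.

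**The case against.** The strongest reply is that adjustment is already planned. The same section includes a Mantel-Haenszel analysis and a logistic regression, logistic regression takes continuous covariates, and age and MMSE are among the listed variables. That stands: a reader might infer that the baseline information is thrown away, and the SAP does not support this. What is missing is a commitment to how the information will be used.

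Three other tempting readings also fail.

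- That the chi-square/Fisher sentence is the declared primary arm comparison. It concerns associations between categorical variables in general. It is the natural test for two proportions, but it is not labelled as such.
- That age and MMSE will be dichotomised. That conversion appears only in the McNemar clause.
- That patients with poor cognition are known to be enrolled. No MMSE threshold is set, but consent, adequate consciousness and the ability to communicate are required, and how widely MMSE varies here is unknown.

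It is also fair to say that the crude test is valid under randomisation, that its error rate already averages over chance imbalance, and that the gain may be nil if the covariates predict little. All of that stands and limits the size of the point. It does not answer the lack of prespecification, which is the SAP's own task and which leaves the choice of adjusted result open.

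**Conclusion.** The point holds as one of prespecification and efficiency. The SAP fixes no baseline covariate in any inferential model, although it collects two obvious candidates on everyone. The likely gain from fixing them is about 0 to 5 points of power near the effect that the sample size implies (30% versus 8%), and perhaps 5 to 8 points at 30% versus 12% if they are strongly prognostic. The clearer benefit is that the result would no longer depend on baseline imbalance in the minority of trials where it is sizeable.

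These figures rest on a 30% control rate, 47 evaluable per arm, two-sided testing and an assumed prognostic strength that the SAP does not give. A material loss of power therefore cannot be demonstrated from the document, and the crude analysis would not be wrong. The change is still worth making because it costs almost nothing.

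**What to change.** In the Statistical analysis section:

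- Name the between-arm comparison of R1 CAM-ICU as a logistic model with arm, age (continuous) and MMSE score (continuous), all forced in with no selection.
- Report the odds ratio and the standardised risk difference, each with a 95% CI.
- Keep the crude chi-square or Fisher test as a supporting analysis, and label stepAIC exploratory.
- Use MMSE scores taken before surgery and projection, and report their timing relative to allocation. Restricting to scores obtained before allocation could exclude every score, because Development of the intervention lists randomisation first.
- With about 18 events and three model terms (about 6 events per term), stop at these two covariates. State in advance whether the fit is ordinary or Firth-penalised, and do not let the choice depend on how sparse the data turn out to be.

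The cost is SAP wording and one model in R, with no new data. The small downside is that the estimate rests on a model, and the likelihood-ratio test may be slightly liberal at this size (up to 5.9% in the simulations).

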### **Instrument**

An "ad hoc" registration sheet is prepared in order to facilitate data collection. The record sheet contained sociodemographic data, surgical and anesthetic characteristics, as well as postoperative and postoperative delirium care. In addition, the CAM-ICU scale as well as the Mini-Mental State Examination is applied to the patients included in the study. The CAM-ICU scale is a validated scale and it is the most frequently used scale to assess the presence of delirium in critical care units, while the Mini-Mental State Examination scale is used to assess the patient's previous cognitive state.

The estimated time for completing the record sheet is 4 minutes and 7 minutes for the administration of each of the both scales. Confidentiality is ensured at all times through alphanumeric coding so as to avoid the recording of their personal data.

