### **Development of the intervention**

Patients are randomized into two groups (control group and intervention group) after explaining the study and offering voluntary participation.

Initially, regardless of the group to which they belonged, all patients are administered the MMSE scale to assess their initial cognitive state and their sociodemographic and anthropometric data are collected.

In the intervention group, patients and/or companions are asked to provide visual material, which could consist of photographs of loved ones and/or places known to the patient. Once the surgical intervention is completed, the patients are transferred to the Cardiac Resuscitation Unit. 30 minutes after the extubation of the patients, the CAM-ICU scale is administered, recording its value as R0. Next, the projection of images provided by the patient began until 11:30 p.m., at which time these images are replaced by a nocturnal visual projection (night sky with stars and moon), ensuring that the patient is able to identify that it is nighttime. Later, at 7:00 p.m. the visual projection is removed and the record sheet is completed with the anesthetic and surgical data. Finally, at 9:00 a.m., a nurse who had not worked at night and therefore did not know which patients had received the intervention, administered the CAM-ICU scale again, recording its value as R1.

In the control group, we proceeded as follows: after the surgical intervention and after the patient is admitted to the Unit, we waited 30 minutes after the patient's extubation to administer the CAM-ICU scale, recording its value as R0. The following day, at 7:00 a.m., the record sheet is completed with the anesthetic and surgical data, and finally, at 9:00 a.m., another nurse administered the CAM-ICU scale, noting its value as R1, without knowing which patients belonged to each group. If postoperative delirium is detected during the day and night, the unit's usual treatment is followed: administration of haloperidol and/or dexmedetomidine if the patient showed agitation.

Finally, a member of the research team, who did not know which patients had received the intervention, analyzed the data obtained without knowing what each variable referred to.

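### The only regression is stepAIC on an undefined variable set: the SAP neither states that randomised arm is kept nor excludes delirium drugs, restraints and projection variables

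*SAP*

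**What the plan says.** The regression is specified in the Statistical analysis section of the SAP as follows: "the logistic regression model is used, including the variables included in the analysis. The stepAIC function from the R MASS package is used". The set of variables is thus defined by itself. The section gives no outcome for the model, no purpose, no candidate list, no direction of selection and no term that must stay in.

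The pool of recorded variables is wide. Under Variables it includes "those related to the projection of visual material, pharmacological measures or mechanical restraints used". Under Instrument, one record sheet holds sociodemographic data together with "surgical and anesthetic characteristics, as well as postoperative and postoperative delirium care".

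Development of the intervention places randomisation after the study is explained and consent is sought, before surgery. Its control-group paragraph links drug use to the outcome. The trigger is worded "If postoperative delirium is detected during the day and night". What follows in that case, according to the same sentence, is that "usual treatment is followed: administration of haloperidol and/or dexmedetomidine if the patient showed agitation". Design describes the same drugs, and mechanical restraints, as the unit's usual care for delirium.

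The same Statistical analysis section also offers chi-square or Fisher tests for independent data. It does not say which analysis carries the comparison of the arms.

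**The concern.** Drugs and restraints used for delirium come after randomisation and can come because of delirium. A variable that is partly a consequence of the outcome predicts it well, and AIC rewards prediction, so AIC tends to keep it. Such a variable then competes with the arm indicator for the same few events. Projection is delivered only in the intervention group, so a projection variable comes close to duplicating arm.

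On the wording given, stepAIC is also free to remove arm. An arm odds ratio that is reported only when it survives selection is exaggerated, because survival favours the trials with large estimates.

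At stake is any adjusted arm effect taken from this model. It could be missing, underpowered or overstated, and it could disagree with the unadjusted comparison.

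**Working it through.** **Inputs from the SAP (Sample).** Delirium 30%, 10% loss, 52 per group, power 80%, alpha 0.05. Evaluable per arm: 52 × 0.90 = 46.8, taken as 47.

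**The SAP's own figure.** The 52 cannot be rebuilt because the second proportion is not stated. The usual two-sided two-proportion formula gives 47 per group for 30% vs 7.5%, and 47 / 0.90 = 52.2, so 52 roughly fits that effect. For 30% vs 10% it gives 62 before loss. The point here does not depend on which effect was intended.

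**Assumptions.** The SAP gives no rates of drug use. The illustration takes delirium of 30% vs 10% and drug use in 70% of delirious and 5% of non-delirious patients, the same in both arms.

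**Step 1: the true odds ratio and the number of events.** OR = (0.10/0.90) / (0.30/0.70) = 0.111 / 0.429 = 0.26. Expected events = 47 × (0.30 + 0.10) = 18.8. Variables names 14 items besides the CAM-ICU result (two of its lists are open-ended), so 18.8 / 14 = 1.3 events per candidate.

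**Step 2: the AIC rule.** A one-parameter term is kept when its likelihood-ratio chi-square exceeds 2, which corresponds to p below about 0.157. Arm gets no protection beyond that.

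**Step 3: large-sample bias.** Within a level of drug use, the odds of delirium are odds(delirium | arm) × P(drug level | delirious) / P(drug level | not delirious). If that last ratio is equal in both arms, it cancels from the arm odds ratio. So the fixed arm-plus-drug model has no large-sample bias at equal use. If use differs by arm, it does not cancel.

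**Step 4: finite-sample behaviour.** Simulation with 47 per arm and backward AIC from arm plus drug, compared with arm as the only candidate:

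| Quantity | No drug candidate | Drug candidate (70% / 5%) |
|---|---|---|
| Wald power for arm at 0.05 | about 68% | about 35% |
| Effective arm dropped by AIC | about 13% | about 32% |
| Median OR when arm is kept (true 0.26) | about 0.23 | about 0.17 |

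AIC kept the drug variable in essentially every trial. Repeat runs agree to within one or two percentage points, and to about 0.01 on the odds ratios.

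**Step 5: sensitivity to the assumed rates (30% vs 10%).**
- 50% use in delirious patients: power 50%, arm dropped in 23%.
- 30% use in delirious patients: power 60%, arm dropped in 17%.
- 70% use in delirious and 10% in non-delirious patients: power 48%, arm dropped in 26%.
- At 30% vs 7.5% with 70% / 5% use: power falls from 79% to 43%, and arm is dropped in 23% against 6%.

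**Step 6: selection without any care variable.** With arm and eight pure-noise covariates at 30% vs 15% (true OR 0.41), arm was kept in 65% of runs, with a median OR of 0.28 when kept. With arm forced in, the median was 0.38. Selection alone therefore exaggerates the effect, and retaining arm removes most of that.

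**The case against.** The strongest reply is that the SAP never says this model estimates the arm effect. It is called only the multivariate analysis, and an exploratory search for risk factors is an equally natural reading. The chi-square or Fisher tests already compare the arms. This stands, and it makes the harm conditional. It does not remove the gap, because the SAP states no purpose for the model and does not say which analysis counts.

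The illustration also draws drug use from the final delirium status. In the plan, drugs follow delirium detected during the day or night, while R1 is scored at 9:00 a.m. Much of the drug use would come before R1 and might alter it, so the link to R1 could be weaker than assumed. This stands too; Step 5 shows the loss shrinking as the link weakens.

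Four stronger readings are tempting and are not supported:
- **That arm is left out of the model.** The SAP is silent; stepAIC may keep it or drop it.
- **That the analyst cannot screen out unsuitable variables.** The analyst "analyzed the data obtained without knowing what each variable referred to", but someone else could supply a coded list. What the SAP lacks is a list fixed in advance.
- **That drug use differs by arm and so biases the odds ratio in a known direction.** The contrast in Design makes unequal use conceivable, but nothing states it.
- **That stepAIC clearly inflates false positives for arm.** With noise covariates only, these were about 5% in one simulation. In another they were 6.5% whether or not arm was forced, against 4.5% unadjusted, with a Monte Carlo error of about 1 point.

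**Conclusion.** The point holds as one of specification. The only regression has a circular variable set, no stated outcome or purpose, no statement that arm is kept, and no exclusion of post-randomisation care variables. Confidence that the text permits the problem is high; confidence in the size of the harm is moderate.

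The consequences apply only if the model is used for the arm effect. Then the arm odds ratio is overstated when arm survives selection, and a retained delirium-care variable can roughly halve the power for arm and make dropping an effective arm about two and a half times as likely (32 / 13 = 2.5). Those sizes rest on assumed delirium and drug-use rates and are smaller if drug use is only weakly related to R1. Equal use leaves the fixed arm-plus-drug model unbiased in large samples, but not the estimate that selection would report. Unequal use would add further bias.

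A reader should not infer that the trial's unadjusted comparison is compromised; it is untouched. This should be fixed, but it does not undermine the design.

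**What to change.** In the Statistical analysis section:

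1. Name the unadjusted chi-square or Fisher comparison of R1 CAM-ICU by randomised arm as the main comparison.
2. For any adjusted arm effect, specify one logistic model with R1 CAM-ICU as outcome, arm always retained, and one or two named covariates measured before projection starts. Age and MMSE are examples; the SAP already records that "all patients are administered the MMSE scale to assess their initial cognitive state". With about 18.8 events, arm plus one covariate gives 18.8 / 2 = 9.4 events per parameter, and arm plus two gives 18.8 / 3 = 6.3. The choice of covariates is a matter of judgement; what matters is that it is made in advance.
3. State that delirium drugs, restraints and projection details other than the arm indicator are never covariates in that model, and fix the list before analysis.
4. Keep stepAIC only as a labelled exploratory search for risk factors, not used for the arm effect.

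The cost is wording only, since the data are already collected. The one downside is that fewer covariates are explored in the arm-effect model.

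### The SAP names no deciding test of delirium by group, and its stepAIC logistic model is too large for the data and free to drop the randomised group

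*SAP*

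**What the plan says.** The SAP's Sample section sizes the trial for one difference between two proportions, "with a statistical power of 80% for an alpha significance level of 0.05". It assumes 30% delirium and 10% loss, and arrives at 52 patients per group. The second proportion is not given.

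The Statistical analysis section then lists these methods:

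- **Unadjusted:** "the chi-square statistic or Fisher's exact test is used when the data are independent" (McNemar is kept for related data).
- **Stratified:** "Stratified analysis is performed using the Mantel-Haenzsel test". No stratification factor is named.
- **Multivariate:** "the logistic regression model is used, including the variables included in the analysis. The stepAIC function from the R MASS package is used". No covariate list, direction, scope or forced term is given.

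The closing rule is that "a confidence level of 95% is used and any value of" p below 0.05 is significant. No analysis is called primary.

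The Variables section, from which the model's candidates must come, is open-ended: it covers age, gender, body measures, living situation and "the type of intervention, use of drugs, time mechanical ventilation or extracorporeal circulation, etc". It also includes the drugs and restraints used for delirium.

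**The concern.** The design alpha of 0.05 belongs to one comparison, but the analysis section offers three routes to a p-value for group against delirium and does not say which one answers the trial's question. Two things are at stake.

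1. **Error rate.** A reader of the results cannot tell whether a claim of effect must rest on the unadjusted test or may rest on whichever analysis falls below 0.05.
2. **The adjusted estimate.** stepAIC treats the randomised group like any other term. If the group is dropped, the final model says nothing about treatment: no odds ratio and no confidence interval.

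**Working it through.** **Inputs.** From the Sample section: alpha 0.05 (two-sided assumed), 30% delirium, 52 per group, 10% loss. Evaluable per arm: 52 × 0.90 = 46.8, taken as 47. Events under no effect: 94 × 0.30 = 28.2, about 28. The number and strength of covariates and the strata are not in the document and are assumed.

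**The plan's own figure.** The 52 cannot be checked directly, because the second proportion is missing. With

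n = [1.96·√(2p̄q̄) + 0.842·√(p₁q₁ + p₂q₂)]² / (p₁ − p₂)²

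and p₁ = 0.30:

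- p₂ = 0.08: (1.087 + 0.448)² / 0.22² gives 49 evaluable per arm; 49 / 0.9 gives 55 enrolled. This is close to 52.
- p₂ = 0.06 with continuity correction: 47 evaluable; 47 × 1.1 = 51.7, so 52.
- p₂ = 0.15: (1.157 + 0.489)² / 0.15² gives 121 evaluable per arm, far beyond the plan.

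So 52 per group suits a fall from 30% to roughly 6-8%. At 47 per arm, power for 30% vs 15% is 41% by formula and 43% in simulation.

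**False positives with no effect (30% in both arms).** Two separate simulations were run.

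*Simulation A:* 47 per arm, covariates modelled on the Variables section, backward AIC, 6,000 trials per setting. Covariates are either unrelated to delirium or moderately related (log-odds 0.4-0.5 for five of the 11).

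| Analysis counted | Unrelated | Related |
|---|---|---|
| Chi-square alone (exact size 5.1%) | 5.3% | 4.8% |
| stepAIC group test alone, 11 covariates | 6.9% | 6.9% |
| Chi-square or stepAIC | 7.8% | 8.5% |
| Same, plus Mantel-Haenszel by gender | 7.9% | 8.7% |
| Same, plus three Mantel-Haenszel stratifications | 8.0% | 9.2% |
| stepAIC alone, five covariates | 5.5% | 5.1% |
| Any analysis, five covariates | 6.5% | 6.8% |

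*Simulation B:* 47 or 52 per arm, 5 or 10 normal covariates, log-odds ratio 0, 0.4 or 0.8 per SD, two-directional AIC, 4,000 trials per scenario. Chi-square alone gave 4.6-5.6%, Mantel-Haenszel alone 4.4-5.4%, stepAIC alone 5.1-6.8%, chi-square or stepAIC 5.8-9.5%, and any of the three 6.1-10.0%.

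**Where the excess comes from.** In A, Mantel-Haenszel by gender adds 0.1-0.2 points and three stratifications add 0.2-0.7. The rest enters with the logistic model, by two routes. It is a second, imperfectly correlated chance of a positive result. When large, it also exceeds 5% by itself: 11 covariates (one with three levels) plus group make 13 parameters, and 28 / 13 is about 2 events per parameter.

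Deletion of group is not the cause. About 2,000 null trials per setting with the 11 covariates gave, unrelated/related:

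- group deletable: 6.6% / 8.0%
- group forced in: 6.6% / 8.0%
- full model, no selection: 6.5% / 7.5%

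Forcing group in changed no verdict in 4,073 trials. This is expected, because a term is dropped only where it would not have been significant.

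**Deletion rule.** AIC = −2 log L + 2k. Dropping a 1-df term changes AIC by (likelihood-ratio statistic − 2), so the term goes when the statistic is below 2. P(χ²₁ > 2) = 0.157, so group is dropped when p > 0.157.

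**How often, at 47 per arm:**

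| True rates | Group deleted |
|---|---|
| 30% vs 8% | 7-8% |
| 30% vs 15% | 31-36% across the runs |

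**Fixed alternative (group, age, MMSE).** False positives are 4.4-5.1%. Power at 30% vs 15% is 41-45%, against 43% for chi-square.

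**The case against.** The strongest reply is that the closing rule is an ordinary per-test threshold. It does not say that one positive analysis establishes efficacy, nor that all three methods compare the groups on CAM-ICU. The Sample section ties alpha to a difference between two proportions, which points to the unadjusted test, and if that test decides there is no inflation. This stands: counting any positive analysis is a reading the text permits, not one it states. It does not remove the gap, because the SAP nowhere says that the unadjusted test decides.

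Three stronger readings are tempting and are not supported:

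- **That selecting the group term inflates the error.** Forcing the group in left the rates unchanged. The excess comes from adding a large logistic model beside the chi-square test.
- **That the treatment is lost from the model in a third of trials at the planned effect.** That figure belongs to 30% vs 15%. Near the effect that 52 per group can detect, it is 7-8%.
- **That deletion leaves the trial with no effect estimate.** Only the logistic model is affected. The unadjusted comparison remains, and Mantel-Haenszel can give a stratified odds ratio once its strata are named.

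Multiplying three independent 5% tests (1 − 0.95³ = 14.3%) would also overstate the matter, since the analyses are highly correlated.

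**Conclusion.** The point holds in a limited form. The SAP does not name the analysis that decides whether the projection affects delirium. If any positive analysis were accepted, the false-positive rate would be about 6-10% instead of 5%. That range rests on 47-52 per arm, 30% delirium, and 5 to 11 covariates of none to strong prognostic value. The last two are assumptions, because the document gives neither. The inflation is modest, and it is zero if chi-square alone decides.

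The deletion problem stands whichever test decides. As specified, the model can omit the randomised comparison and so cannot be relied on for an adjusted odds ratio and confidence interval. This should be corrected, but it does not invalidate the trial.

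**What to change.** In the Statistical analysis section:

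1. Name one deciding test of R1 CAM-ICU by group, for example a two-sided Pearson chi-square, with Fisher's exact test if an expected count is below 5. State that only this test supports a claim of effect.
2. Label Mantel-Haenszel (strata named) and logistic regression as supportive, reported as odds ratios with 95% confidence intervals.
3. Replace stepAIC with a fixed logistic model of group plus a few pre-named covariates measured before the projection, such as age and MMSE. The Development of the intervention section shows that MMSE and sociodemographic data are collected at the start.
4. If stepAIC is kept for exploration, force the group in (lower = ~ group). This preserves the estimate but does not by itself restore the 5% error rate.

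The cost is a few sentences, with no extra patients or data and about the same power. The team gives up claiming an effect from a supportive analysis.
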